Study Description: We will randomize 1500 adults aged 60+ to 10 weeks of one of three Step 1 strategies: aripiprazole augmentation, bupropion augmentation, or switch to bupropion. Those who do not attain remission in Step 1 will be randomized to 10 weeks of one of two Step 2 strategies: lithium augmentation or switch to nortriptyline. Those who complete acute treatment will be followed in a one-year continuation. This pragmatic RCT will be carried out in real-world clinical settings. Primary care and mental health clinical partners will provide treatments, with decision support from the study team.

Study population: Participants will be non-demented older adults aged 60+, with equal proportions aged 60-70 and 70+, with current major depression that has failed to respond to 2+ adequate antidepressant trials. We will recruit across five regions: St. Louis and rural Missouri; Los Angeles City and County; Western Pennsylvania; New York City; and Toronto and rural Ontario. Two-thirds of the sample will be women and 70% white, 15% black, 10% Latino, and 5% other racial groups.

Patients will be identified from clinical networks at each of the five participating centers. Our two primary mechanisms of recruitment will be through screening and referrals. We will screen through clinical networks using Electronic Medical Records (EMR) and will contact all patients in practices aged 60 and older who in the recent past were prescribed or are currently taking antidepressants. Referrals will be elicited from practitioners and through in-practice

OPTIMUM Protocol Version 3.0 2019-03-04 Final Version

advertisements to patients and their caregivers specifically asking if the doctor, patient, or caregiver describes the clinical situation as treatment resistant or difficult to treat.

Primary/secondary outcomes: Psychological well-being is the patient-centered effectiveness outcome and remission from depression is the clinician-focused effectiveness outcome. Secondary patient-reported outcomes include physical function and social participation. Safety will be monitored through serious adverse events as well as falls and fall-related injuries. As well, the study will test how aging influences the relative benefits and risks of antidepressants for TRD. Additionally, a qualitative study of patient and clinician partners will provide the lived experience of TRD and antidepressant strategies.

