most experts believe that one of the most efficient ways to decrease suicidal risk in older depressed individuals is to treat their depression. Furthermore, all participants will be formally assessed frequently throughout the study. All sites have a 24/7/365 on-call system with geriatric psychiatry back-up. If the study personnel identify that a participant has become acutely suicidal, this participant will be referred to a mental health professional for further evaluation and treatment. This may lead to a clinical intervention that is lifesaving and may not have occurred had the participant not been participating in the study. We have included a Suicide Risk Management protocol to assess and reduce suicide risk in the manual of procedures as well as a Quick Suicide Safety Screening that may be used during phone pre-screening.

Body Composition Measurement (Washington University site only):

For participants with a pacemaker or a prosthesis that uses any other type of battery-powered or electrical power implant, there is a chance that the measurement of body composition could cause interference with the device. In order to protect from that risk, participants should not take part in the body composition measurement if they have a battery-powered or electrical implant. Participants with a history of abnormal heart rhythms will be reviewed by a medical doctor to make sure that the body composition measurement will not worsen their condition.

1.i Potential Benefits

Participants may or may not benefit from being in this study. Changing medication strategies may provide relief from symptoms of depression. Results from this study will provide doctors and patients with knowledge about the risks and benefits of antidepressant medications for older adults, so that they can make informed choices to manage depression.

1.j Early Withdrawal of Subjects

Participants will be asked to continue in the study for follow-up regardless of their and their physician's adherence to the medication recommendations from the study team. Participants who discontinue study medications for tolerability reasons will be asked to complete the appropriate Acute Phase End Assessments for their phase of the study (see Section F5). Participants who end Step 1 treatment early due to tolerability issues will be invited to proceed to Step 2 after completing Acute Phase End Assessments.

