Participants who choose to withdraw from the study early will be asked to complete the appropriate final visit for their phase of the study (Step 1 Week 10, Step 2 Week 20, or Continuation Month 12).

Withdrawal from the study for any reason, including study completion, will be documented in the Electronic Case Report Form.

Participants' reasons for withdrawal will be summarily reviewed by each site's IRB at Continuing Review and at DSMB meetings.

E Medication Strategies and Decisional Support

1.a **Description of Decisional Support**

The pragmatic, comparative effectiveness design research participants continue to receive ongoing care, management, and prescriptions from their own physicians. The research team will

randomly assign participants to the well-established, evidence-based, standard of care medication strategy conditions. The research team will assess participants for symptoms and tolerability by phone every two weeks during acute treatment. The research team will make a recommendation for medication dosing that the treating physician can override or ignore. The Manual of Procedures for this study will describe how the study team will communicate the randomization assignment and any recommended changes to the treating physician. This decision support is greater than is seen in usual clinical care. Patients highly recommended it, and a similar measurement-based approach has worked well in our prior studies in late-life depression.

- Dose adjustment is done by the treating clinician with support from researchers:
 - If PHQ-9 score is 6 or greater, and side effects are absent or well-tolerated: increase the dose.
 - If PHQ-9 score is 5 or less, or side effects are enough that participant cannot tolerate a dose increase: keep dose the same.
 - If side effects are such that participant needs a dose decrease: decrease dose back to previous.
 - o If side effects are intolerable such that participant needs a medication change: end step and move on to the next step (or remove from study if in step 2).
- Clinicians and patients have flexibility: they may decide to exit Step 1 or Step 2
 treatment early (e.g., due to tolerability issues). Clinicians are allowed to coprescribe
 other medications as well. The Manual of Procedures for this study will contain the
 communication plan for how the treating physician will communicate any changes or
 new medications back to the study team.

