- Phone Call with Local Research Team (approximately 10 minutes)
 - o PHQ-9
 - Spontaneous side effect report & severity
 - Falls Assessment
 - Adherence
 - o Counselling about adherence and management of side effects.
 - AE reports done as needed.
 - Decision support staff contact study MDs when needed (e.g. if confusion about whether to increase antidepressant dose).
 - Decision support staff contact participant's clinical provider with recommendations;
 also will typically tell patient the recommendations.

F5 Acute Phase End Assessments

- Step 1 Week 10, Step 2 Week 10, or upon early withdrawal (if possible)
 - If there is a long delay between the Step 1 Week 10 assessment and the initiation of Step 2, the participant may be asked to repeat some or all of the Step 1 End assessments.
- *In addition to Decision Support assessments, local research team will conduct the following assessments (in person if possible; approximately 1 ½ hour):
 - NIH Toolbox Psychological Well Being (may be conducted via phone or Redcap survey)
 - PROMIS Physical Function (may be conducted via phone or Redcap survey)
 - o PROMIS Social Participation (may be conducted via phone or Redcap survey)
 - NIH Cognition and Motor Batteries (may be foregone for participants living in remote locations)
 - Weight (self-reported)
- Central Rater Assessments (by phone; approximately 30 minutes. WU participants may do in person or by phone)
 - o MADRS

F6 Continuation Assessments

- Months 4, 8, and 12 after completing acute treatment in Step 1 and/or 2 as indicated.
- Participants who relapse in Continuation after Step 1 may be invited to participate in Step 2; and then continuation subsequently.
- Local Research Team Assessments (in person if possible; approximately 1½ hour)::
 - NIH Toolbox Psychological Well Being (may be conducted via phone or Redcap survey)
 - PROMIS Physical Function (may be conducted via phone or Redcap survey)
 - o PROMIS Social Participation
 - Weight
 - NIH Cognition and Motor Batteries (Month 12 only; may be foregone for participants living in remote locations)
- Central Rater Assessments (by phone; approximately 30 minutes)
 - o MADRS
 - Falls & Related Injuries
 - Spontaneous side effects and severity(discuss with local sites if needed)
 - Adherence

F7 Genetic Testing

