A priori, specific plans for data analysis correspond to major aims and will be directed by Co-I [name], professor of biostatistics at the coordinating site.

We will follow the intention-to-treat (ITT) principle. In other words, patients who receive coprescribed medications stop randomized medication, or switch to a different medication will continue to be followed. To confirm that ITT findings represent the "true" data on effectiveness, safety, and tolerability of management strategies, we will conduct a sensitivity analysis that will compare ITT to per-protocol findings.

H1a (Psychological Well-Being): We will use a repeated measures 2*2*3 ANOVA with age (60-70, >70), time (baseline, end of Active phase of Step 1) by treatment group (3 levels). Specific time* treatment group contrasts will compare the changes across pairs of treatment groups. These tests will be conducted with a significance level of .05/3. We will include site as a strata in all analyses. For those who proceed to Step 2, analogous repeated measures 2*2*2 ANOVA will be used with a significance level of .05 for the time*treatment group comparison.

H1b (remission): Corresponding 2*3 (age by treatment group) generalized linear models with a logit link function will be computed for the dichotomous outcome of remission.

In the **continuation phase** we will explore the long-term effectiveness of antidepressants: We will test for preservation of psychological well-being and other quality of life variables, and sustained resolution of depressive symptoms, by mixed effects repeated measures models.

We will also test for sustained remission by measuring relapse in each arm. Relapse will be defined as meeting DSM 5 criteria for a major depressive episode, as determined by an Independent Evaluator who will confirm the diagnosis by conferring with a study investigator. We will carry out Cox models examining time to relapse and time to dropout, to examine for treatment inferiority (i.e., whether one antidepressant strategy produces poorer long-term outcomes). Based on our prior research we don't have an empirical basis to posit a specific arm as inferior. Therefore, although these analyses are important to our stakeholders, we describe them as exploratory.

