2.2.3. Scope

This Statistical Analysis Plan will be the guiding document for the quantitative analyses that will be conducted in the OPTIMUM study.

3. Study Methods

3.1. General Study Design and Plan:

Participants will be recruited from five regions with diverse and representative populations encompassing approximately 708 adults. The five regions are: St. Louis and rural Missouri; Los Angeles City and County; Pittsburgh and Western Pennsylvania; New York City; and Toronto and rural Ontario. Participants will be non-demented adults aged 60+, with equal proportions aged 60-70 and 70+, with current major depression that has failed to respond to 2+ adequate antidepressant trials. Two-thirds of the sample will be women and 86% White, 7% Black, 8% Latino/Hispanic, and 4% other racial groups.

All recruited adults will be randomized to 10 weeks of one of three Step 1 strategies: aripiprazole augmentation, bupropion augmentation, or switch to bupropion. Those who do not attain remission in Step 1 or those who do not qualify for Step 1 will be randomized to 10 weeks of one of two Step 2 strategies: lithium augmentation or switch to nortriptyline. Those who complete acute treatment will be followed in a one-year continuation, with assessments every four months. This pragmatic RCT will be carried out in real-world clinical settings. Primary care and mental health clinical partners will provide treatments, with decision support from the study team.

Patients will be identified from clinical networks at each of the five participating centers. Our two primary mechanisms of recruitment will be through screening and referrals. We will screen through clinical networks using Electronic Medical Records (EMR) and will contact all patients in practices aged 60 and older who in the recent past were prescribed or are currently taking antidepressants. Referrals will be elicited from practitioners and through advertisements to patients and their caregivers.

An additional mechanism of recruitment will be through IRB-approved hospital network registries and social media advertisements and posts on Facebook and Instagram. Potential participants who see Facebook ads and want to participate in the study can click on the Facebook ad and it will direct them to a secure and encrypted survey website using Redcap to collect name, phone number, and email address. Research study staff will contact the potential participants to screen them for study eligibility.

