5.4. Withdrawal/follow-up

5.4.1. General withdrawal rules

Participants will be asked to continue in the study for follow-up regardless of their and their physician's adherence to the medication recommendations from the study team. Participants who discontinue study medications for tolerability reasons will be asked to complete the appropriate Acute Phase End Assessments for their phase of the study. Participants who end Step 1 treatment early due to tolerability issues will be invited to proceed to Step 2 after completing Acute Phase End Assessments.

Participants who choose to withdraw from the study early will be asked to complete the appropriate final visit for their phase of the study (Step 1 acute endpoint, Step 2 acute endpoint, or Continuation Month 12).

Statistical Analysis Plan OPTIMUM

Withdrawal from the study for any reason, including study completion, will be documented in the Electronic Case Report Form.

Participants' reasons for withdrawal will be summarily reviewed by each site's IRB at Continuing Review and at DSMB meetings.

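### Protocol E 1.a removes intolerant Step 2 participants from the study, against the follow-up and ITT rules, so continuation and later SAE data could be lost

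*Protocol*

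**What the plan says.** Protocol E 1.a lists the dose actions that go with decision support. For side effects so bad that the medication must change, the action is to "end step and move on to the next step (or remove from study if in step 2".

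Four other places govern the same situation:

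- Protocol 1.j (Early Withdrawal of Subjects): "Participants will be asked to continue in the study for follow-up regardless of their" own or their physician's adherence to the recommendations. It adds that those who "discontinue study medications for tolerability reasons will be asked to complete the appropriate Acute Phase End Assessments" for their phase, and does not mention removal.
- SAP 5.4.1 repeats that rule: "Participants will be asked to continue in the study for follow-up".
- Protocol H1 defines ITT so that patients who "stop randomized medication, or switch to a different medication will continue to be followed".
- SAP 4.3 repeats the ITT definition.

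Entry to the continuation year is tied to completing acute treatment. Protocol A1 says "Those who complete acute treatment will be followed in a one-year continuation", SAP 3.1 says "Those who complete acute treatment will be followed in a one-year continuation, with assessments every four months", and Protocol F6 times the visits at "Months 4, 8, and 12 after completing acute treatment in Step 1 and/or 2 as indicated". The change log (K5, V2.4) records that continuation was widened from remitters to all participants.

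**The concern.** The trigger for removal is intolerable side effects, which is itself a safety outcome arising after randomization. A site that acts on the words of E 1.a stops observing the people who tolerated their assigned drug worst. The same bullet keeps an intolerant Step 1 participant in the trial, moving to Step 2, so only the lithium versus nortriptyline comparison is exposed.

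The analysis at stake is H2a. SAP 6.2 compares arms on serious adverse events with a Cox model (Andersen-Gill extension) over the acute phase and the continuation together. That model takes censoring to be unrelated to later event risk, given the covariates. Removal for intolerance may break that assumption, and could do so unequally if the two drugs differ in tolerability; the protocol lists different side-effect profiles for them. Continuation falls, well-being and MADRS would end for the same reason.

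**Working it through.** The plan states no figure on this point, so the check is mainly a comparison of texts, followed by a count of what one removed person would lose.

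**1. Do the rules address the same person?** Yes. E 1.a covers a Step 2 participant who needs a medication change because of intolerance. Protocol 1.j covers those who stop study medication for tolerability. H1 and SAP 4.3 cover those who stop or switch. The E 1.a case falls inside all of them, with the opposite instruction.

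**2. Does any text limit the clause to treatment?** No. The next bullet in E 1.a speaks of leaving Step 1 or Step 2 treatment early, so the protocol has wording for stopping treatment only, but the challenged clause says study. The SAP does not repeat the clause and does not cancel it.

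**3. Is an early Step 2 stopper clearly routed to Continuation?** Not clearly. A1, SAP 3.1 and F6 all speak of completing acute treatment. The F2 footnote allows the step-end assessment at dropout, which suggests a step can be finished early. The V2.4 log entry points to follow-up for everyone, but it is framed around remission status, not intolerance.

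**4. What would one removed person lose, read literally?**

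- Continuation assessments: months 4, 8 and 12, so 3 of 3. These include the falls assessments that the central raters make in that year (F2 footnote, F6).
- SAE follow-up: Protocol G 1.b collects SAEs to the later of 30 days after the last dose or the follow-up visit. Assume the last dose is at exit and no later visit takes place.
  - Continuation counted from exit: 365 − 30 = 335 days (335/7 = 47.9 weeks).
  - Exit at week 2, Continuation counted from the scheduled week 10: (10 − 2) × 7 = 56 days, so 365 + 56 − 30 = 391 days (55.9 weeks). F6 does not state this way of counting.
  - Both are upper bounds, since they assume that 1.j is not followed.
- Acute falls calls: none attributable to the clause. F4 schedules these calls every two weeks during acute treatment, so they stop when the step ends, whether or not the person is removed.

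**5. What stays protected?** Protocol 1.j and F5 still ask for end-of-phase assessments on early exit (F5 adds if possible), so MADRS and well-being may be captured. SAP 6.3 counts early stoppers without a MADRS as non-remitters.

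**6. Can the effect on the trial be sized?** No. It needs the share of each Step 2 arm removed for intolerance and the later event risk of those removed. The documents give neither.

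**The case against.** The strongest defence is that this is one loose parenthesis in a list of dose actions, in a section whose recommendations the treating physician may override or ignore. The section actually headed early withdrawal gives the correct rule for this very case, the SAP repeats it, and the ITT text agrees. In such a list, removal may only have meant that no further study step exists. The V2.4 change to follow all participants in Continuation fits that reading. Rewording also changes little if conduct is finished, as the note in D1 about a figure updated after study completion suggests, and SAP 6.3 already plans dropout reasons and sensitivity analyses.

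Much of this stands. Continued follow-up is the stated design, and the clause is plausibly a leftover. But it is in the current text and tells staff what to do, and nothing in the documents says which instruction prevails. The Manual of Procedures might, but it is not among them. SAP 6.3 is specific only for MADRS; other outcomes rest on its general commitment to sensitivity analyses, and a tabulation by Step 2 arm is not promised.

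A reader might also infer that one to four of the five two-weekly falls calls are lost to removal. They are not, since those calls end with the step. SAP 6.1.1 even says that acute falls were not collected, although SAP 6.2 plans to model them.

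**Conclusion.** The conflict is real and should be corrected. Its established size is modest: for each intolerant Step 2 participant handled literally, the three continuation assessments and SAE follow-up beyond 30 days after the last dose would be lost. The Step 2 SAE comparison could then be informatively censored, provided that sites acted on the clause and that tolerability differs between lithium and nortriptyline. The documents establish neither condition.

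Three stronger conclusions are tempting and not supported:

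- That participants were in fact removed. The documents contain an instruction, not a record of what sites did.
- That the Step 2 well-being or remission result is biased. Exit assessments are requested, and missing remission status has its own rule. Step 1 is unaffected, and SAP 6.1.1 calls all continuation analyses secondary.
- That about a year of SAE data, or a stated amount of power, is lost. The 335 to 391 days are a ceiling per person that assumes 1.j is ignored. A power figure would need an invented removal rate, and the 400 per arm in the protocol's Step 2 power table belongs to a plan that SAP 3.3 has since cut back.

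**What to change.** In E 1.a, replace the parenthesis on Step 2 with: *or, if in Step 2, end Step 2 treatment, complete the Acute Phase End Assessments and enter Continuation follow-up (months 4, 8 and 12, with SAE and falls collection) unless the participant withdraws consent*. In F6, time the visits *after completing or ending acute treatment*. This costs one clause and two added words, and uses visits already scheduled.

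If conduct is complete, report by Step 2 arm how many participants had follow-up ended under this instruction, and include them explicitly in the sensitivity analyses planned in SAP 6.3. The reason for withdrawal (Protocol 1.j) and the person who made the decision (SAP 6.3) are to be recorded already, so the cost is one table. It would show whether the clause affected anyone, and whether it did so unequally.

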Yet, in spite of the high stakes for public health, the comparative risk/benefit ratio of antidepressants is entirely unstudied in older adults with TRD. This stands in contrast with numerous studies in younger adults.²⁵⁻²⁹ This evidence gap was highlighted in critical reviews^{30,31}

that found a complete lack of evidence in this age group. The sole exception is our recent randomized controlled trial (RCT) of aripiprazole augmentation in older adults.^{2,32}

C Study Objectives

The study aims to close the evidence gap on late-life depression in three ways:

C1 Aim 1: Effectiveness

Examine the comparative benefits and risks of antidepressant strategies (augmentation and switching) in older adults with TRD.

Effectiveness outcomes: psychological well-being and remission from depression Safety outcomes: serious adverse events, falls, and fall-related injuries

C2 Aim 2: Effects of Aging

Explore how age, and age-related variables (medical comorbidity, cognitive problems) change the balance of benefits vs. risks.

C3 Aim 3: Maximize Stakeholder Engagement

We will maximize stakeholder engagement to ensure relevancy to providers and patients alike.

C4 Rationale for the Selection of Outcome Measures

OUTCOME	WHEN AND HOW MEASURED	RATIONALE
Psychological well-being is the patient-centered effectiveness outcome (Hypothesis 1a [H1a]).	In Acute, beginning and end of Step 1 (and Step 2); in Continuation months 4, 8, 12.	Psychological well-being encompasses satisfaction, happiness, cognitive engagement,
Secondary quality of life measures are self-reported physical function and social participation.	Measured by NIH Toolbox* (Psychological Well-being) and PROMIS* (Physical function, Social participation). Assessed by independent rater**	and meaning/purpose. It is a critical dimension of quality of life, recommended by patient stakeholders in focus groups as an outcome that matters.
Remission is our clinician- focused effectiveness outcome (H1b): reduction of depressive symptoms below a threshold (MADRS≤10). This goal of treatment is a consensus among practitioners. ^{53,54}	In Acute, beginning and end of Step 1 (and Step 2); in Continuation, months 4, 8, 12 Assessed by independent (blind) rater** via 20-30 minute phone interview.	The MADRS measures 10 areas of depressive symptoms. It is a standard outcome in antidepressant studies. Patient stakeholders described this assessment as "very important" for assessing effectiveness.

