NIH Toolbox Cognition and Motor batteries -@done if participant able to be seen in person		х						Х						х			х
Cognition battery including Attention/exec function (flanker and dimsional change card sort), Episodic memory (Picture seq memory), working memory (List sorting), Processing speed (pattern comparison). Baseline only: Language (Oral reading recognition) Motor battery including Dexterity (pegboard), Strength (using grip dynamometer), Balance,																	
gait speed																	
Psychological well-being (NIH Toolbox self-report measure)		х						х						х	X	х	х
Physical Function (PROMIS)		х						х						х	Х	х	х
Social Participation (PROMIS)		х						х						х	Х	х	x
AE and SAE collection (collected anytime the event occurs)																	
Anxiety (PROMIS)		х															
Done by central rater pool at WU by phone:																	
MADRS		х						х						х	х	х	х
*Typically Week 10; or upon dropout																	
**Central rater pool will assess side effects, falls, and adherence during continuation; local s	ites can do	additional	decisi	on sup	ort cal	lls "as n	eeded	during"	this tim	ne							

F3 Baseline

- Participant signs (or returns signed) informed consent form; all elements of informed consent have been discussed and participants' questions answered.
- Local Research Team Assessments: (in person if possible; approximately 3 hours)
 - MINI MDD & Bipolar Modules
 - PHQ-9 (If more than 7 days has elapsed since the PHQ-9 was done at pre-screen.)
 - Suicide History, Risk & Protective Factors
 - Baseline Side Effects
 - Expectations for Adherence
 - Behavioral Therapy Assessment
 - Falls & Related Injuries (history)
 - Height and Weight (self-reported)
 - If indicated by pre-screen: DAST-10
 - o If indicated by pre-screen: AUDIT
 - NIH Toolbox Psychological Well Being
 - o PROMIS Physical Function
 - o PROMIS Social Participation
 - PROMIS Anxiety
 - NIH Cognition and Motor Batteries (in person assessments may be foregone for participants living in remote locations)
 - o ATHF
 - o CIRS-G
 - Medical Conditions and Medication List (study doctor to review before randomization)
 - Confirm inclusion/ exclusion criteria are met
 - Randomize participant; provide initial decision support per randomization status to participant's doctor.
- Central Rater Assessments (by phone; approximately 30 minutes)
 - o MADRS

F4 Decision Support Calls

- Every 2 Weeks During Acute Treatment: Step 1 Weeks 2, 4, 6, 8, 10* & Step 2 Weeks 2, 4, 6, 8, 10*

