3.2. Randomization

Randomization of participants will be implemented in REDCap, using a randomized block design by alternating blocks of 3 and 6 within strata by site (i.e., St Louis vs. Pittsburgh), referral source (primary care vs. specialty mental health) and age (<70 vs >70).

Only assessors of outcome measures will be blinded. Assessors will be instructed to not ask, and participants instructed to not share the treatment to which they were assigned. Participants, providers, and other research staff will not be blinded to treatment conditions.

In this pragmatic design where all levels of adherence are allowed, participants will be considered randomized assuming they meet the eligibility requirements at screening (including any safety screens as applicable) and they have been given a randomization assignment (i.e., even if participants never took a dose of the randomized medication, they will be included in the analysis).

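### The MADRS blind is put at risk at continuation months 4, 8 and 12, because the central rater pool also collects study-drug adherence and side effects in the same contact

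*Protocol*

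**What the plan says.** Protocol D2 1.g limits blinding to the outcome assessors; participants, providers and other research staff know the assignment. The MADRS row of C4, which covers the acute steps and continuation months 4, 8 and 12, reads "Assessed by independent (blind) rater via 20-30 minute phone interview". SAP 3.2 adds a safeguard: "Assessors will be instructed to not ask, and participants instructed to not share the treatment to which they were assigned".

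In the F2 schedule the MADRS stands under the heading "Done by central rater pool at WU by phone". The double-asterisk footnote to the same schedule says "Central rater pool will assess side effects, falls, and adherence during continuation". F6 has one block for each continuation visit, headed "Central Rater Assessments (by phone; approximately 30 minutes". It lists the MADRS, falls, side effects and adherence, in that order. The side-effect line reads "Spontaneous side effects and severity(discuss with local sites if needed".

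The acute phase is arranged differently. F4 puts side effects, falls and adherence in a "Phone Call with Local Research Team (approximately 10 minutes", and the central-rater block in F5 lists only the MADRS.

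**The concern.** Assignment is open to everyone except the rater, so the rater's blind is the main protection against detection bias in the MADRS. At months 4, 8 and 12 the same pool is given two topics that can disclose treatment, and has permission to talk to staff who know it. The SAP tells assessors not to ask about treatment, while F6 gives them questions that invite the answer.

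At stake is the credibility of the long-term MADRS comparisons. F6 lists no other depression scale at these visits. A rater who learns the drug at month 4 may also rate the same person at months 8 and 12.

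**Working it through.** The plan states no figure on this point, so the check is mainly a comparison of sections.

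**1. Who collects what**

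| Item | Acute phase (F4, F5) | Continuation (F2 footnote, F6) |
|---|---|---|
| MADRS | Central pool, only item in its block | Central pool |
| Side effects | Local team | Central pool, may confer with local sites |
| Adherence | Local team | Central pool |
| Falls | Local team | Central pool |

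The acute phase separates the blinded rating from the treatment-related items. Continuation merges them.

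**2. Can the added items carry treatment information?**

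- *Adherence.* Section E 1.a and 1.i define it as taking the medication and dose that the study recommended. An answer can easily name the drug, although it need not.
- *Side effects.* In Section E 1.c to 1.f, akathisia is listed only for aripiprazole and increased thirst only for lithium. Most other effects overlap. Dry mouth is listed for bupropion, lithium and nortriptyline; constipation for aripiprazole, bupropion and nortriptyline; tremor or shakiness for aripiprazole, bupropion and lithium. Bupropion augmentation and bupropion switch share one table, so listed side effects cannot separate those two arms.
- *Contact with sites.* Local staff are unblinded under D2 1.g, so a discussion of side effects is a second route.

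**3. What protection is stated?** SAP 3.2 forbids asking about or sharing the assignment. Neither document gives a drug-neutral adherence script for continuation, a required order of items, a separate MADRS rater, or a check on whether the blind held.

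**4. Which outcomes are exposed?** SAP 6.1.1 makes all continuation analyses secondary. The MADRS enters through the depressive-symptom trajectory and through the secondary relapse definition (MADRS ≥15). The primary relapse definition uses PHQ-9 criteria. The Step-end MADRS that decides H1b falls in the acute phase, where the local team takes the sensitive items.

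**5. Illustration of size.** Assume follow-up MADRS among remitters is roughly normal with mean μ and SD σ, and ratings in one arm drift down by d points. Then

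P(MADRS ≥15) ≈ 1 − Φ((14.5 − (μ − d)) / σ).

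For μ = 8, σ = 6, d = 0: (14.5 − 8)/6 = 1.083, which gives 13.9%. For d = 1: (14.5 − 7)/6 = 1.25, which gives 10.6%.

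| Assumed μ, σ | d = 0 | d = 1 | d = 2 | Change, d = 1 | Change, d = 2 |
|---|---|---|---|---|---|
| 8, 6 | 13.9% | 10.6% | 7.8% | 3.3 points | 6.1 points |
| 10, 7 | 26.0% | 21.6% | 17.7% | 4.4 points | 8.3 points |
| 12, 8 | 37.7% | 33.1% | 28.7% | 4.6 points | 9.0 points |

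The mean, SD and drift are all assumed; none comes from the documents. The calculation is for a single visit, whereas the plan uses a Cox model for time to relapse.

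**The case against.** The strongest reply is that nothing here proves disclosure. Adherence can be asked as missed doses without naming a drug, and side effects are spontaneous reports. SAP 3.2 instructs both parties. F6 lists the MADRS first; if that is also the order of the call, each visit's rating is finished before the sensitive questions. The documents speak of a pool, so the same rater may not return. Co-prescribing and switching are allowed, so a drug mentioned at month 8 need not be the assigned one. The footnote text behind the C4 rater mark is not in the copy reviewed, and the Manual of Procedures may say more.

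Most of this stands. It rules out saying that the ratings are unblinded, or that adherence cannot be taken without revealing the drug. It does not remove the risk, because the order and the change of rater are possible readings and not requirements.

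Three further inferences are tempting but unsupported:

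- *That H1b is contaminated when a relapser enters Step 2.* Step 2 is a new 1:1 randomization, so knowing the Step 1 drug does not reveal the Step 2 arm.
- *That the Step-end option in F5, "WU participants may do in person or by phone", is a leak.* It differs from the telephone-only wording elsewhere, but the central rater still does the rating and no route to disclosure is shown.
- *That the bias must favour augmentation.* SAP 2.2.2 hypothesizes better effectiveness with augmentation, but for continuation Protocol H1 says there is no empirical basis for naming an inferior arm.

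**Conclusion.** The point holds as a risk to the blind at months 4, 8 and 12. The sections conflict in substance: the rater is to be blind and not to ask about treatment, yet is given study-drug adherence, side effects and a line to unblinded staff. The reading that all four items belong to one contact is the natural one from F6, though the protocol does not say that one person must do them all.

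The reach is limited to the continuation MADRS trajectory and the MADRS ≥15 relapse analysis, both secondary. H1b at Step 1 and Step 2 end and the PHQ-9 relapse definition do not depend on these ratings. No sample size, power or alpha figure changes. The direction and size of any bias are unknown. The 3 to 5 point change (one-point drift) and the 6 to 9 point change (two-point drift) show only how sensitive a threshold outcome would be under the assumed means and SDs. The 1.8-point detectable MADRS difference in Protocol H2 is not a yardstick for this, since it is set for the acute steps at 500 or 400 per group. The case for change rests on the low cost of closing the gap.

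**What to change.** In F2 (double-asterisk footnote) and F6, have the local research team collect adherence and side effects at months 4, 8 and 12. The central rater keeps the MADRS and falls, which agrees with the independent assessment of falls in C4 and SAP 6.1.2.

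If the items must stay in the central call, require the MADRS to be completed and locked in REDCap before any adherence or side-effect question. Where the pool allows, use a different rater at the next visit; locking alone protects the current rating but not later ones.

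Keep the route by which a rater passes side-effect information to the site, since it serves safety monitoring. Make it one-way: rater to local site, after the MADRS is locked, with no treatment information returned.

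The cost is mainly wording. Two downsides should be accepted openly. Under the first option, continuation side effects would be recorded by unblinded staff, as they already are in the acute phase. F6 also lets some local measures be done by survey, so a short local call may be needed where no live contact takes place.
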